Specific Aims 1- 5, Effectiveness of ZNS in the Treatment of Alcohol-Dependent Veterans: We propose to conduct a 16 week, randomized, double blind, placebo-controlled study of ZNS in **N=160** regularly heavy drinking veterans with AD in the context of a minimal ambulatory psychosocial treatment aimed at enhancing adherence to medication (Medical Management, MM), (68). We will recruit and enter **160** subjects with which the study will be adequately powered. *All subjects must be currently alcohol dependent. The target dosage for ZNS is 500mg/day, which will be titrated up over the first 7 weeks of treatment, with dosage increases based on tolerability. The titration schedule will start with 100mg daily, increased to 200mg/day after the first week,*

and then increased by 100mg/day every 2 weeks to the **target dose of 500mg/day**. Subjects will then begin 9 weeks at the target dose with the option to increase to 600mg daily after two weeks at target if treatment response is suboptimal and there are no significant side effects (no current moderate to severe AE's with 500mg daily). Dosing will remain flexible with respect to the time of day that the medication is administered, in order to maximize compliance and minimize the impact of adverse effects. The dosage will be held or reduced based on the appearance of moderate-to-severe adverse effects. **Following the seven week titration phase, subjects will begin the 9 week period of active treatment on the target dose, followed by up to 2 weeks of tapering and discontinuation of the medicine, and a return for follow-up at three months post-treatment. The dosing is also flexible in that it will allow subjects to continue on at less than the target dose based on tolerability, but subjects must be able to tolerate at least 200mg/day (two pills). Also, if subjects are not having moderate to severe side effects during the treatment phase, and have not yet reached 600mg/day, they may be increased by up to 100mg every 2 weeks if it is felt that they may benefit further from it. This will allow maximum flexibility and optimal dosing.**

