6.D.2. Visit 1 (Baseline Visit): N= 160 subjects will be randomly assigned to receive either ZNS (80 subjects) or placebo (80 subjects). We will use blocked stratified randomization with treatment site (VA Connecticut versus Bedford) and the use of other psychotropic medications (e.g., antidepressants) as the stratification variables, with block sizes of 4 in each stratum to achieve treatment balance throughout the randomization process. Within 21 days after the screening visit, eligible subjects undergo a two-hour pre-treatment assessment (described below). At the baseline visit, subjects will complete a packet of questionnaires. Subjects will receive their first medication management session and first supply of study medication during a treatment session (visit 1) scheduled on the same day, following completion of the baseline assessments.

Subjects will begin study medication (i.e., ZNS or matching placebo) at an initial dosage of 100mg/day. All subjects will be asked to bring any remaining capsules and the study medication container to their next and all subsequent clinic visits, so that capsule counts can be used to measure compliance. The subject begins 6-week titration phase, during which the dosage will be titrated up as indicated above and in Table 1. Subjects will be paid a nominal but fair amount of money in compensation for all visits, including follow-up visits. Table 1 shows the titration schedule:

TABLE 1: Medication Titration Schedule

Week	Placebo	Zonisamide dose
1	One capsule daily	100mg QHS
2	Two capsules daily	200mg QHS
3	Two capsules daily	200mg QHS
4	Three capsules daily	300mg QHS
5	Three capsules daily	300mg QHS
6	Four capsules daily	400mg QHS
7	Four capsules daily	400mg QHS
8-9	Five capsules daily	500mg QHS (Target dose)
10-16	Five or Six capsules daily, 7 weeks duration	Continue 500mg daily or optional increase to 600mg QHS, 7 weeks duration
17-18	TAPER: Decrease capsules by one a day every 3 days, over a period of up to 15 days	TAPER: Decrease dose 100mg every 3 days, over a period of up to 15 days

Table 1 notes: 7 weeks of titration to the 500mg daily target dose. 9 weeks at the target dose with the option to increase to 600mg daily after two weeks at target if treatment response is suboptimal and there are no significant side effects (no current moderate to severe AE's with 500mg daily).

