6.D.4. Visits 2-17 (Treatment and End-of-Treatment Visits): Subjects will return weekly for study visits to meet with the research nurse, complete questionnaires, and receive medical management (MM, described below). At study midpoint (i.e., 8 weeks after starting medication), another CBC, and chemistry/electrolyte panel (including a serum GGT), will be obtained. Urine drug screens will be checked weekly, and pregnancy tests (in all females of reproductive potential) are repeated monthly. At the end of week 16 (endpoint), subjects will complete the packet of questionnaires and will be interviewed by the research evaluator concerning their alcohol-related symptomatology using the Alcohol Use Disorders section of the SCID over the past 30 days. Subjects will also be interviewed by the research nurse about their use of concomitant medications, occurrence of adverse events, compliance with the protocol, and their assessment of the effectiveness and acceptability of the treatment procedures. A blood sample for measurement of serum GGT and metabolic labs will be obtained to provide an index of potential hepatic effects and to assess the validity of self-reported drinking. A urine drug screen and urine pregnancy screen (in all females of reproductive potential) will be obtained at this time as well. The nurse and study physician will monitor continuing adverse events to their resolution. Subjects requesting (or clearly needing) additional treatment for alcohol problems are (if clinically indicated) discontinued from the study protocol and referred to local treatment centers. Similarly, at the end of the treatment trial, subjects whose drinking requires continued treatment will be referred for such treatment. All subjects will be asked to complete an end-of-treatment evaluation to facilitate planned intention-to-treat analyses. All subjects will be informed of these procedures prior to study enrollment.

6.D.5. Visit 10b (Stress Lab Session 2): This visit will occur between weeks 8-16 of being on the study medication. The session will use the same audio tapes created for the baseline stress lab and the session will be identical to the baseline stress lab (assessments), with the exception of the randomized order of the presentation of the audio tapes.

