6.F.1. Laboratory/Medical Assessments. The purposes of these assessments are: 1) to screen subjects for medical exclusion criteria, 2) to monitor medication adherence (retrospectively), 3) to assess potential side effects of medication, and 4) as objective measures of drinking. Prior to entrance into the study, each subject will receive a physical examination, urinalysis and urine toxicology, urine Ethyl glucuronide, CBC, and a chemistry panel (which includes electrolytes, liver enzymes, bilirubin, creatinine, and BUN). Women of childbearing potential will undergo serum pregnancy testing prior to beginning treatment and then urine pregnancy testing monthly thereafter (i.e., every 4 weeks) to identify women who become pregnant, so as to avoid exposing the fetus to the study medication. After 4 weeks on medication, and at the study midpoint (after treatment week 8) and at the end of the 16-week treatment phase, serum chemistry (including bicarbonate level), liver function tests, CBC, and serum GGT will be repeated. In order to monitor possible medication side effects, weight and vital signs (blood pressure and pulse) will be obtained at each treatment visit. Urine drug screens will be obtained at the initiation of the study to identify individuals who use drugs regularly, and will be repeated weekly thereafter. General metabolic and hematologic labs will be drawn more frequently if needed in order to monitor the health of subjects during the study. We will obtain blood phosphatidylethanol (PEth) levels at baseline, and weeks 8, 12 and 16 and urine Ethyl Glucuronide (EtG) levels at screening and weeks 4, 8, 12, 16, to use as biomarkers of alcohol use.

Table 2: Schedule of Assessments (See Table 3 for Stress Lab Assessments)

	SC	BL	Study Week																
			1	2	3	4	5	6	7	8	9	10	11	12	13	14	15	16	18
Surveys/Procedures																			
Overview and Consent	X																		
Demographics	X																		
Locator Information	X																		
SCID-IV	X																		
Medical History/ Physical/Psych Exam	X																		
AUQ		X	X	X	X	X	X	X	X	X	X	X	X	X	X	X	X	X	X
BDI		X	X	X	X	X	X	X	X	X	X	X	X	X	X	X	X	X	X
CIWA	X	X	X	X	X	X	X	X	X	X	X	X	X	X	X	X	X	X	X
C-SSRS		X	X	X	X	X	X	X	X	X	X	X	X	X	X	X	X	X	X
PCL-5		X	X	X	X	X	X	X	X	X	X	X	X	X	X	X	X	X	X
SAFTEE		X	X	X	X	X	X	X	X	X	X	X	X	X	X	X	X	X	X
STAI		X	X	X	X	X	X	X	X	X	X	X	X	X	X	X	X	X	X
TLFB/measures of treatment received	X	X	X	X	X	X	X	X	X	X	X	X	X	X	X	X	X	X	X
MM		X	X	X	X	X	X	X	X	X	X	X	X	X	X	X	X	X	X

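### No CBC or bicarbonate is scheduled between weeks 8 and 16, the period of highest dose; a subject can spend up to 49 days at 600 mg before the next scheduled panel, although blood is already drawn at week 12

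*Combined protocol and SAP*

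**What the plan says.** **Laboratory schedule.** Section 6.F.1 requires CBC and a chemistry panel before entry. It repeats CBC, liver tests, GGT and chemistry with bicarbonate at three points on treatment: "After 4 weeks on medication, and at the study midpoint (after treatment week 8) and at the end of the 16-week treatment phase". Section 6.D.4 restates the middle one: "At study midpoint (i.e., 8 weeks after starting medication), another CBC, and chemistry/electrolyte panel". Section 6.F.1 adds "General metabolic and hematologic labs will be drawn more frequently if needed", without a trigger or an interval. The same section plans a separate blood draw for an alcohol biomarker: "We will obtain blood phosphatidylethanol (PEth) levels at baseline, and weeks 8, 12 and 16".

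**Dosing.** The Table 1 notes give "7 weeks of titration to the 500mg daily target dose", so 500 mg starts in week 8. For weeks 10 to 16 the table reads "Continue 500mg daily or optional increase to 600mg QHS, 7 weeks duration". That step needs a suboptimal response and no current moderate or severe adverse effect. Section 6.A separately lets subjects without such effects who are still below 600 mg go up: "they may be increased by up to 100mg every 2 weeks if it is felt that they may benefit further from it". It also provides that "The dosage will be held or reduced based on the appearance of moderate-to-severe adverse effects". None of these rules refers to a laboratory result.

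**Purpose of the panels.** Section 8.B names rare hematologic reactions and metabolic acidosis, and gives repeated blood counts and bicarbonate as the safeguard, so that changes are found early. Section 8.C adds that repeated laboratory tests serve to catch reactions that subjects do not readily report.

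**The concern.** The scheduled checks are furthest apart when planned exposure is greatest. The panels at weeks 4 and 8 cover titration and the first week at target. Almost all of the target-dose period, and any time at 600 mg, is first covered by the panel at the end of treatment. By then the taper is starting, so the result can no longer guide dosing at target.

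The changes that these tests look for may give no symptoms. Weekly SAFTEE, vital signs and weight do not measure blood counts or bicarbonate. A rule that acts on visible side effects does not cause blood to be drawn for a silent change. At stake is how soon such a change would be seen, judged against the plan's own aim of early detection.

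**Working it through.** **Convention.** Day 0 is the first dose, and week w ends on day 7w. A panel is drawn before any dose change on the same day. The inputs are Table 1 and its notes, 6.F.1, 4.B.3.b, and the 21-day screening-to-baseline window in 6.D.2.

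**1. Reproduce Table 1.** Weeks 1-7 are below 500 mg (7 weeks), weeks 8-16 are at target (9 weeks), and weeks 10-16 allow 600 mg (7 weeks = 49 days). All three match the table and its notes.

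**2. Panel days.** 7 × 4 = 28, 7 × 8 = 56, 7 × 16 = 112. From first dose the intervals are 28, 56 − 28 = 28, and 112 − 56 = 56 days. The first interval does not start at a panel. The pre-treatment panel may be up to 21 days before baseline, so that panel-to-panel gap is 28 to 28 + 21 = 49 days. The last gap is double the week 4 to 8 gap.

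**3. Position of the week-8 panel.** 500 mg starts on day 7 × 7 = 49, so the panel follows 56 − 49 = 7 days at target. The target period lasts 112 − 49 = 63 days, and 56 of them (56/63 = 89%) come after that panel. Section 4.B.3.b puts steady state within 14 days of a stable target dose, so 7 days may be too short. The end-of-treatment panel is the first scheduled one sure to reflect steady state at 500 mg.

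**4. Time at 600 mg.** The earliest start is after two weeks at 500 mg: day 49 + 14 = 63. The wait to the next scheduled panel is 112 − 63 = 49 days. Any later start gives a shorter wait, so 49 is the maximum under Table 1.

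**5. With a week-12 panel (day 84).**

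| Quantity | Now | With week 12 |
|---|---|---|
| Gaps from week 8 to week 16 | 56 | 28, 28 |
| Wait after 600 mg starts on day 63 | 112 − 63 = 49 | 84 − 63 = 21 |
| Wait after 600 mg starts on day 84 | 112 − 84 = 28 | 112 − 84 = 28 |
| Longest wait, any start from day 63 | 49 | 28 |

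**6. Sensitivity to the reading.**
- Section 6.D.2 also speaks of a 6-week titration. That would open 600 mg on day 42 + 14 = 56 and make the maximum 112 − 56 = 56 days, so 49 is not the high end.
- In the copy of Table 2 that I could read, the monitoring-lab marks fall at weeks 4, 7 and 15. The PEth row is also displaced from its text (7 and 11 for 8 and 12), so I follow 6.F.1. Taken literally, the gap is still 105 − 49 = 56 days, with 105 − 63 = 42 days at 600 mg.
- Section 6.D.4 does not name CBC among the endpoint bloods, but 6.F.1 does. I follow 6.F.1.

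**The case against.** The case for the present schedule has substance.

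- **Panels follow dose change.** On schedule the dose is 300 mg at the week-4 panel, 500 mg at week 8 and at most 600 mg at week 16. The rise is 500/300 = 1.67-fold between the first two and 600/500 = 1.2-fold between the last two. Testing more often while the dose moves fastest is coherent. This stands as a rationale. It does not explain why the week-8 panel comes only 7 days into the target dose.
- **600 mg may be uncommon.** The pilot mean maximal dose was 430 mg/day against a 500 mg target (4.B.3.c), and 600 mg is optional here. This stands: 49 days is a maximum, and the share of subjects reaching 600 mg is not given. The 56-day gap applies to every subject, whatever the dose.
- **Serious reactions are rare.** Section 8.B says so, and reports no serious adverse events in the pilot. This stands, and limits how much weight the point can bear.
- **Other safeguards exist.** Extra draws are allowed, side effects are reviewed weekly, and the principal investigator evaluates every adverse event (8.F). These act on what is noticed or measured. None requires blood between weeks 8 and 16.

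A reader might infer that the plan breaks its own promise. It does not: 8.B commits to several time points and sets no interval, and screening plus weeks 4, 8 and 16 meets that. A reader might also build a path in which a subject held at a low dose is raised at every opportunity after week 8, giving a large dose multiple between panels. Section 6.A permits this, but nothing suggests that it is common, so it should not measure the gap.

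**Conclusion.** The gap is real and is a matter of monitoring design. On the Table 1 schedule no CBC or bicarbonate is scheduled for the last 56 of 63 target-dose days. A subject raised to 600 mg at the first opportunity can spend at most 49 days at that dose before the next scheduled panel.

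It is tempting to read this as evidence that 600 mg is unsafe or that subjects will be harmed. The documents do not support that. They give no dose-risk relation, place 600 mg within the range usually used in epilepsy, and expect it to be well tolerated. The day counts measure a delay in looking, not a risk, and the plan contains no error here.

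The conclusion rests on three assumptions: Table 1 governs dosing, 6.F.1 governs the panels, and no as-needed draw happens to fall in the window. It supports a low-cost improvement, not a correction on which the trial depends.

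**What to change.** Add CBC and serum chemistry with bicarbonate to the week-12 blood draw already taken for PEth. In 6.F.1, list the on-treatment safety panels as weeks 4, 8, 12 and 16, and mark week 12 in the monitoring-labs row of Table 2.

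The cost is at most 160 extra panels (one for each of the 160 subjects) and the review of their results. No visit or venipuncture is added, and the allowed doses and the primary analysis do not change.

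The change is partial: a subject raised to 600 mg at week 12 or later waits as long as now, up to 28 days. I would not add a physician sign-off before late increases. The documents give no threshold for it, it would largely duplicate existing review, and for an on-schedule increase on day 63 it would look only at the week-8 result.

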Psychiatric diagnosis. The Structured Clinical Interview for DSM-IV (SCID-I) will be used to classify patients according to the presence or absence of standard psychiatric disorders (73).

(b). Areas Assessed At Intake And During Each Treatment Visit:

Alcohol use patterns. The Time-Line Follow-Back Assessment method (TLFB), (74) will be used to estimate current alcohol consumption and drinking at intake and also weekly during treatment. This interview procedure will provide quantity/frequency of alcohol consumption data for each day during the period prior to the interview. Data on cigarette smoking will also be obtained using the TLFB. The Clinical Global Impression scale (CGI) will be used to assess progress in treatment monthly. The Clinical Institute Withdrawal Assessment (CIWA-Ar) will be used to facilitate assessment of withdrawal, and decisions regarding appropriateness for study entry and continuation with respect to physical dependence will be made based on the judgment of study physicians.

Psychological symptoms. The Beck Depression Inventory is generally regarded as a sensitive, self-report measure of depressive symptoms, and will be administered at each treatment visit to provide a means to monitor symptoms clinically. The Spielberger State Anxiety Inventory will be used to measure anxiety symptoms weekly (75). Suicidal ideation will be assessed at each visit using the Columbia Suicide Severity Rating Scale (76). Subjects with any current symptoms of suicidal ideation will be assessed by a licensed study clinician (i.e., an M.D., or Ph.D. psychologist), and referred immediately for further treatment if necessary. Subjects deemed by study clinicians to be at too high a risk of suicide to be managed in the outpatient setting will be discontinued from the study and referred immediately for treatment. PTSD symptoms will be measured by the Clinician-Administered PTSD Scale for DSM-V (CAPS-5) and the PTSD Checklist for DSM-V (PCL(77)-5). CAPS-5 will be conducted at baseline, week 8, week 16, and follow-up; PCL-5 will be conducted at baseline, weeks 1-16 and follow-up.) (78)

Desire to drink. Desire to drink will be assessed at each treatment visit with the Alcohol Urge Questionnaire (AUQ), (79).

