Medication administration and medication-related adverse events. In addition to regular monitoring of vital signs, subjective reports of side effects will be monitored weekly using a list of adverse effects that have previously been reported for ZNS. A commonly used form (SAFTEE) for assessing and tracking side effects, their severity (on a scale of 1-5), and resolution, will be implemented.

Measures of treatment received. At each treatment visit, patients will be asked to return the unused portion of study medication. Staff will record the number of contact hours patients have been exposed to any treatment outside of the study that is related to their drinking and any self-help group attendance.

(c). Areas Assessed At Intake And At Treatment Endpoint:

Alcohol-related problems. The Short Index of Problems (SIP), which measures alcohol-related problems in five domains, will be used to assess change in such problems reported by patients in this trial (80). The SIP has good internal consistency, good concurrent validity, and adequate stability. The RAND 36-Item Health Survey, a 36-item self-report measure of life functioning in various domains, will be completed at study baseline, endpoint, and follow-ups. The Quality of life enjoyment and satisfaction survey (Q-LES-Q) will be used to assess quality of life in subjects.

(d). Areas Assessed Only At Treatment Endpoint:

Endpoint rating form. This is to be completed by the research assistant when the patient leaves treatment, indicating the patient's level of functioning at termination, and to chronicle as specifically as possible the reasons for termination (i.e., dropout, symptomatic failure, failure to comply with treatment), other circumstances behind the decision to terminate treatment, and who made the decision to terminate the treatment (patient, therapist, physician).

Brief 30 day assessment of Alcohol Dependence Symptoms. Subjects will be asked about AD symptoms for the last 30 days of treatment to assess for remission from the diagnosis.

Assessment of tolerability, efficacy, and masking questionnaire. This is a five-page questionnaire that measures the subject's subjective evaluation of the efficacy and tolerability of the medication, provides an opportunity for feedback on the study, and evaluates the success of the medication blinding procedure.

(e). Areas Assessed daily:

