We will use the percentage of subjects with no heavy drinking days (**PSNHDD**) as the primary outcome variable. This outcome is the FDA recommended endpoint for pivotal trials, and is described in Falk et al., (2010). The PSNHDD can be derived from each subject's TLFB data. An important initial consideration in considering effectiveness will be to identify baseline differences between groups that may have occurred despite randomization. **Successful outcomes during the treatment trial will be defined in terms of a statistically significant difference on the primary outcome measure: PSNHDD, compared during the 8 weeks of active treatment at the target dose, allowing for a 6 week grace period for the medication titration.** For all analyses, heavy drinking days will be defined as follows; for men > 5 drinks in a day and for women > 4 drinks in a day. Patients will be followed irrespective of whether they continue to receive medication treatment, so that analysis will include all data available for the 8-week treatment period. The analysis will be **intent-to-treat**, and dropouts will be considered as having relapsed to heavy drinking. We will use a logistic regression analysis with PSNHDD as a categorical dependent variable. Medication condition (placebo or ZNS) will be the main independent variable, and we will include the variables of early onset of alcoholism (EOA, binary), and the use of additional psychotropics (e.g., antidepressants, a binary variable) as covariates. The α will be set at .05 for the primary outcome variable. Between site differences will be explored.

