6.I.3. To examine the tolerability of ZNS compared to placebo (Specific Aim 2): An important consideration in evaluating the outcome of this pilot study is the tolerability of ZNS in subjects. To examine tolerability in the present study, the frequency of specific groups of adverse effects of a moderate-to-severe nature will be tabulated and compared to placebo using Fisher's Exact Test. We will also compare ZNS and placebo groups on the number of subjects for whom medication treatment is discontinued due to adverse effects. Overall dropout rates will be examined, as well as measures of medication adherence.

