Data and Safety Monitoring Board (DSMB): [name]., a board certified psychiatrist and the principal investigator of the proposed study, will be charged with the duty of determining the severity rating of adverse events. The study staff (P.I., co-investigators, clinical research coordinator) is responsible for collecting and recording all clinical data. As these results are collected, all toxicities and adverse events will be identified, graded for severity and assigned causality, reported to the required entities, and compiled for periodic review. After assigning causality, the P.I. will decide the course of action for the study participant. The P.I. will evaluate every adverse event and determine whether it affects the risk/benefit ratio of the study and whether modifications to the protocol or informed consent form are required. Serious adverse events will be reported to the West Haven VAMC/Bedford IRBs, as well as the DSMB, within 48 hours.

Reports of adverse events, protocol deviations, and any other relevant safety information (drop outs, etc.) will be reported to the DSMB every 6 months. DSMB members will review and decide whether the study should continue as planned, or if changes are needed, or if the study should be stopped. Teleconferencing will be performed to facilitate these discussions between the DSMB and research team as needed. The review process will be documented and reported to IRBs.

The DSMB is composed of persons not otherwise affiliated with the clinical trial who are experienced in various aspects of the conduct of clinical trials for the treatment of addictive disorders. We propose three investigators located here in Connecticut who are not directly involved in this trial – [name]., Ph.D., [name]., and [name]. as the membership of the DSMB. These three clinicians have appropriate expertise in substance abuse and psychopharmacology for this study. None of these three are directly involved with this proposed trial and consequently should not pose a conflict of interest. The members of the DSMB and all study Investigators will complete Conflict of Interest forms created by the HSS in accordance with NIH guidelines.

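### Section 6.I.3 compares moderate-to-severe adverse effects between arms without using the pre-dose SAFTEE grade, so complaints that persist from baseline would dilute a real excess on zonisamide

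*Combined protocol and SAP*

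**What the plan says.** Section 6.F.2(b), headed "Areas Assessed At Intake And During Each Treatment Visit", describes the instrument: "A commonly used form (SAFTEE) for assessing and tracking side effects, their severity (on a scale of 1-5), and resolution, will be implemented". In Table 2 the SAFTEE row is blank at screening and marked at baseline, weeks 1-16 and week 18.

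The baseline form precedes dosing. Section 6.D.2 has subjects receive their "first supply of study medication during a treatment session (visit 1) scheduled on the same day, following completion of the baseline assessments".

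Section 6.I.3 gives the analysis: "the frequency of specific groups of adverse effects of a moderate-to-severe nature will be tabulated and compared to placebo", using Fisher's exact test. It does not mention the baseline form, new onset, worsening or attribution to drug. The same section also compares the number of subjects discontinued for adverse effects, overall dropout and adherence.

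The nearest thing to a restricting rule is in section 8.F, where "all toxicities and adverse events will be identified, graded for severity and assigned causality, reported to the required entities". That serves safety reporting, and 6.I.3 does not limit its counts by it. No section defines a treatment-emergent effect.

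**The concern.** The effects listed for zonisamide in section 8.B (somnolence, anorexia, dizziness, headache, nausea, agitation or irritability) are plausible before the first dose in this population. Entrants are regular heavy drinkers (6.C). Depressive disorders, PTSD and other anxiety disorders are admitted (4.B.2), and antidepressants are allowed (6.E.5). The weekly form works from a list of effects already reported for the drug, so it will elicit such symptoms whatever their cause.

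Leaving the baseline form itself out of the count does not solve this. A moderate headache present at baseline and still present at week 1 is recorded at week 1. Randomization makes such background complaints equal between arms on average, and that equality is what pulls the risk ratio toward 1.

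Tolerability is an Aim 2 outcome and part of the stated case for zonisamide over topiramate. A finding of no difference that owed something to background complaints would look like support for that case.

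**Working it through.** The plan gives no rate, power or sample size for this comparison, so there is no figure of its own to reproduce.

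**Inputs from the documents**
- Arm size: "N= 160 subjects will be randomly assigned to receive either ZNS (80 subjects) or placebo (80 subjects"), section 6.D.2.
- Illustrative rates: somnolence 17% vs 7%, section 8.B. These come from epilepsy add-on trials and are not restricted to moderate-to-severe events.
- Significance level: section 6.I.2 says alpha "will be set at .05 for the primary outcome variable". None is stated for tolerability. I used two-sided .05; the Bonferroni correction that 6.I.2 plans for secondary outcomes would lower power under either count.

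**Assumptions**
- b is the share of each arm with the complaint at moderate-to-severe level at baseline. The documents give no value, so a range is shown.
- Every baseline complaint persists to at least one post-baseline visit.
- 17% and 7% are the new-effect rates e among subjects free of the complaint at baseline.

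**Formulas**
- All effects counted: b + (1-b)e.
- New effects only: (1-b)e, over all 80 subjects.
- Power: exact for Fisher's test, by enumerating both binomials at n = 80 per arm.

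At b = 10%, the all-effects rates are 0.10 + 0.90 × 0.17 = 25.3% and 0.10 + 0.90 × 0.07 = 16.3%, a risk ratio of 1.55. The new-effects rates are 0.90 × 0.17 = 15.3% and 0.90 × 0.07 = 6.3%, a risk ratio of 2.43.

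| b | All effects | Risk ratio | Power | New effects only | Risk ratio | Power |
|---|---|---|---|---|---|---|
| 0% | 17.0% vs 7.0% | 2.43 | 42% | 17.0% vs 7.0% | 2.43 | 42% |
| 5% | 21.2% vs 11.7% | 1.82 | 30% | 16.2% vs 6.7% | 2.43 | 39% |
| 10% | 25.3% vs 16.3% | 1.55 | 23% | 15.3% vs 6.3% | 2.43 | 37% |
| 20% | 33.6% vs 25.6% | 1.31 | 15% | 13.6% vs 5.6% | 2.43 | 32% |
| 30% | 41.9% vs 34.9% | 1.20 | 11% | 11.9% vs 4.9% | 2.43 | 26% |

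In this model the absolute difference is (1-b) × 10 points under either count. The baseline grade recovers the risk ratio and removes the extra variance, which is where the power gain comes from. The model gives baseline cases no chance to count as new. If the drug worsens an existing complaint, a baseline comparison picks that up, whereas a plain count has already scored the subject.

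**Sensitivity**
- Half persistence, with all-effects rates b/2 + (1-b)e: power counting all effects is 27% at b = 10% (instead of 23%) and 14% at b = 30% (instead of 11%).
- Rates halved to 8.5% vs 3.5%: 16% at b = 0; at b = 10%, 9% for all effects against 13% for new effects only.
- b = 2% with 17% vs 7%: 36% against 41%.

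**The case against.** The strongest reply is that the plan is silent, not wrong. It speaks of side effects under a heading about medication-related events, tracks them to resolution and has causality assigned. An analyst might drop pre-dose complaints without being told to. That stands in part: a reader might infer that the plan counts every effect regardless of origin, and it does not say so. Nor does it say the opposite, and the causality judgment is not carried into 6.I.3.

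A reader might also infer that frequencies are to be summed over up to 18 forms per subject, breaking the independence that Fisher's test needs. The documents do not support this. A two-arm Fisher's test points to one entry per subject, and the next sentence of 6.I.3 compares numbers of subjects.

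It is likewise tempting to say that week-18 effects must be kept apart because they follow the taper. Section 6.I.3 does not say that they are pooled, and Table 5 counts the taper within 18 weeks on medication. Separating them is a reporting choice.

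The magnitude is fairly challenged. The baseline share has no source, full persistence is the case least favourable to the plan's count, and the rates are borrowed. At 26% to 39% power after the fix, sample size limits this comparison whichever count is used. Discontinuations due to adverse effects, also compared in 6.I.3, are largely untouched. These points limit the size of the problem; they do not change its expected direction.

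**Conclusion.** The concern holds as a gap in 6.I.3: a pre-dose severity grade is collected and the between-arm comparison does not use it. If the pre-existing share is the same in both arms, the risk ratio moves toward 1 and power falls. In a single trial, chance imbalance at baseline could shift the result either way.

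In the illustration the loss runs from 9 percentage points of power (39% to 30%) at a 5% baseline share to 15 points (26% to 11%) at 30%. This rests on full persistence, on epilepsy add-on rates that include all severities, and on an assumed baseline share. Lower rates or partial persistence shrink it, and at a 2% share it is about 5 points. The documents do not allow the actual loss to be stated, and they do not show that dilution would be the main reason for a null result. The change is worth making because the data are already scheduled.

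**What to change.** In 6.I.3, state that a subject is counted once per effect group if, at any post-baseline visit, the effect is moderate or worse and graded higher than on that subject's own baseline SAFTEE. Compare the numbers of such subjects between arms by Fisher's exact test. A table of baseline grades by arm would let readers see how common pre-existing complaints were and whether they were balanced. Showing week-18 effects separately is optional.

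The cost is a sentence or two in the analysis plan and a small programming change. No new data, visits or assessments are needed.
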